3.1. Trial Design

This is an exploratory randomised trial and feasibility trial of RET plus Pulse protein distribution versus RET plus Spread protein distribution.

3.2. Trial Setting

The trial will take place in the Wellcome Trust Clinical Research Facility. Participants will be recruited through the Birmingham 1000 Elders database, a list of adults aged 65 years and over, who have given their permission to be contacted regarding research studies. The custodian of the database will provide contact details for a list of potentially eligible participants based on inclusion criteria. Potential participants will be sent a copy of the participant information sheet along with an invitation letter, which will include a telephone number and email address to contact the study team directly. Potential participants may also be reached through local community groups and leaflets left in public places, and again this will include details to contact the study team directly. Researchers will ask participants to complete a screening health questionnaire over the phone to determine eligibility, and those eligible will be invited to attend a meeting at the Clinical Research Facility. At this meeting, participants will be given the opportunity to ask any further questions, and consent will be obtained. Blood pressure will be measured and the MMSE completed to determine eligibility. After consent, the participant will be asked to complete a 3-day food diary and to wear and activity monitor for 7 days, and a date will be scheduled to being the intervention. Following this initial meeting the participant be randomised to either RET plus Pulse distribution or RET plus Spread distribution.

4. Eligibility

4.1. Inclusion Criteria

Inclusion criteria are: Aged 65 years or over; female; ambulatory (with or without walking aids).

[name] has over 25 y experience of recruiting older participants to studies of exercise and muscle function. Given that confirmation of eligibility in this low-risk study does not require the interpretation of medical notes/ history or a physical examination, [name] is suitably qualified to confirm eligibility. However, any queries about eligibility will be forwarded to the study team's medical expert ([name]) before a decision is taken.

4.2. Exclusion Criteria

Exclusion criteria are based upon previously published criteria for exercise studies and include:

- Already engaging in regular exercise (at least twice a week)
- History of myocardial infarction within previous 2 years
- Cardiac illness: moderate/ severe aortic stenosis, acute pericarditis, acute myocarditis, aneurysm, severe angina,
- Clinically significant valvular disease, uncontrolled dysrhythmia, claudication within the previous 10 years

Trial name:	The effects of protein distribution and resistance exercise training on the muscle of older adults					
Protocol version number:	6.0	version date:	10-Apr-17	Page:	13 of 31	

- Thrombophlebitis or pulmonary embolus within the previous 2 years
- History of cerebrovascular disease (CVA or TIA) within the previous 2 years
- Treatment with anticoagulants (Warfarin, rivaroxaban, apixaban, dabigatran) and antiplatelets (dipyridamole, clopidogrel, prasugrel, ticagrelor, glycoprotein IIb/IIIa antagonists). Nb. those regularly taking aspirin will be asked to stop for 3 days prior to biopsies and restart the day after
- Acute febrile illness within the previous 3 months
- Severe airflow obstruction
- Uncontrolled metabolic disease (e.g., thyroid disease or cancer)
- Significant emotional distress, psychotic illness or depression within the previous 2 years
- Lower limb fracture sustained within the previous 2 years; upper limb fracture within the previous 6 months; non arthroscopic lower limb joint surgery within the previous 2 years
- Any reason for loss of mobility for greater than 1 week in the previous 2 months or greater than 2 weeks in the previous 6 months
- Resting systolic pressure >200 mmHg or resting diastolic pressure >100mmHg
- Poorly controlled atrial fibrillation
- Poor (chronic) pain control
- Moderate/ severe cognitive impairment (MMSE <23)
- Renal impairment (Stage 4 or 5)

5. Consent

It will be the responsibility of the Investigator to obtain written informed consent for each participant prior to performing any trial related procedure. Written, informed consent will be obtained from potential participants by one of the investigators (i.e., the CI, the research nurse or the PhD student after appropriate training). A Participant Information Sheet (PIS) will be provided to facilitate this process. Investigators will ensure that they adequately explain the aim, trial treatment, anticipated benefits and potential hazards of taking part in the trial to the participant. They will also stress that participation is voluntary and that the participant is free to refuse to take part and may withdraw from the trial at any time. The participant will be given at least one week to read the PIS and to discuss their participation with others outside of the site research team. The participant will be given the opportunity to ask questions. If the participant expresses an interest in participating in the trial they will be asked to sign and date the latest version of the Informed Consent Form (ICF).

The Investigator will sign and date the form. A copy of the ICF will be given to the participant, a copy will be filed in the medical notes, and the original placed in the Investigator Site File (ISF). Once the participant is entered into the trial, the participant's unique trial identification number will be entered on the Informed Consent Form maintained in the ISF.

At each visit the participant's willingness to continue in the trial will be ascertained. Throughout the trial the participant will have the opportunity to ask questions about the trial. Any new information that may be relevant to the participant's continued participation will be provided. Where new information becomes available which may affect the participants' decision to continue, participants will be given time to consider and if happy to continue will be re-consented. Re-consent will be documented in the medical notes. The participant's right to withdraw from the trial will remain. With the participant's prior consent, their General Practitioner (GP) will also be informed that they are taking part in the trial.

Trial name:	The effects of protein distribution and resistance exercise training on the muscle of older adults					
Protocol version number:	6.0	version date:	10-Apr-17	Page:	14 of 31	

Details of all participants approached about the trial will be recorded on the Participant Screening/Enrolment Log and with the participant's prior consent, their General Practitioner (GP) will also be informed that they are taking part in the trial.

Trial name:	The effects of protein distribution and resistance exercise training on the muscle of older adults				
Protocol version number:	6.0	version date:	10-Apr-17	Page:	15 of 31

6. Enrolment and Randomisation

6.1. Enrolment/Registration

Prior to consent, participants will complete a health questionnaire over the telephone to determine eligibility. This will be repeated during the consent meeting to ensure no information has been missed, and blood pressure will be measured and the MMSE completed. After consent and prior to randomisation, participants will complete a 3-day food diary and wear an activity monitor for 7 days. In terms of retention, the study is relatively short.

6.2. Randomisation

Participants will be randomised in advance by [name] (UHB Statistician) using a computer generated programme, and concealed in sequentially numbered opaque envelopes. Blocked randomisation will be used for the first 20 participants to ensure at least n=10 in each group.

6.3. Blinding

Due to the nature of the intervention, blinding will not be used. The intervention is protein distribution, and as this is to be achieved by dietary manipulation, participants will be aware of which protein distribution they are receiving.

7. Trial treatment / intervention

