2.2. Outcome Measures

All outcome measures will be made by members of the study team (i.e., research nurses, the PhD student).

The primary outcome measure will be muscle protein synthesis

Secondary outcomes are:

- Serum inflammatory markers (IL-1, IL-6, IL-8, TNF-alpha, and the anti-inflammatory cytokine IL-10)
- Leg extension strength in each leg
- Food diaries
- Feasibility of the trial, including participants' willingness to be randomised, number of eligible participants, number of participants recruited, compliance with the study diets, adherence to exercise and the time taken to collect data

Muscle biopsies will be taken from the thigh at baseline and 2 weeks to measure muscle protein synthesis; at baseline a sample from one thigh will be taken, and at 2 weeks a sample from each leg will be taken, for comparison between exercised and non-exercised legs (see intervention). Saliva samples will also be taken at these times, and an additional saliva sample after 1 week, to allow calculation of MPS. Serum inflammatory markers and 1-RM leg extension strength will be measured at baseline and 2 weeks, and the analysis metric will be change from baseline. Physical activity level will be measured before the start of the study to characterise the population. 3-day food diaries will be completed at baseline and in the final days of the intervention to determine compliance to the diet plan, and participants will be asked to complete a daily questionnaire to confirm whether they have eaten one of the study meals for each meal of the day (yes/no answers). All assessments will take place in the Wellcome Trust Clinical Research Facility.

Trial name:	The effects of protein distribution and resistance exercise training on the muscle of older adults					
Protocol version number:	6.0	version date:	10-Apr-17	Page:	12 of 31	

3. Trial Design and Setting

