7.3. Dosing Schedule

The protein distribution interventions will be administered through the participants' diets. Participants will be given a diet plan to follow, which will provide 1.2 g.kg⁻¹.day⁻¹ protein in either a Pulse or a Spread distribution.

RET will be consist of a unilateral leg extension programme, delivered in one-on-one sessions with a member of the study team three times per week.

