8.3. Trial Procedures

Muscle biopsies; performed by trained member of the study team. If participants regularly take aspirin they will be asked to stop this 3 days prior to each biopsy and restart the day after the biopsy.

Venepuncture; performed by trained research nurse.

1-RM leg extension strength test; established procedure; incremental increases in load until only one repetition can be completed

Physical activity (ActivPAL accelerometry); assessors will be trained.

Serum inflammatory markers will be measured using the Luminex system, and assessors will be trained.

8.3.1.Sub studies

None proposed

9. Adverse Event Reporting

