13.2. Analysis of Outcome Measures

All data will be entered into a database. Using SPSS Statistics for Windows, Version 21.0. Armonk, NY: IBM Corp., data analysis will be conducted by the PhD student on both an intention to treat and per protocol basis (i.e. values for all measurements, completed at least 75% of exercise sessions, and complied with the study diet). Comparisons are planned between Pulse and Spread distribution groups for change in all outcome measures. In the case of MPS, a comparison between trained and untrained legs is also planned. All data will be checked for normality and appropriate log transformations applied prior to *t*-tests for primary and secondary outcome measures.

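### Section 6.3 rules out blinding for every role on a reason that covers only participants, leaving assay staff, the day-14 strength tester and the analyst with no stated masking

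*Protocol*

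**What the plan says.** Protocol Section 6.3 is unqualified: "Due to the nature of the intervention, blinding will not be used". The reason that follows is that "participants will be aware of which protein distribution they are receiving", because the diets are delivered by changing what they eat.

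Other sections assign the work:

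- **Measurement (2.2).** "All outcome measures will be made by members of the study team (i.e., research nurses, the PhD student" and so on; the same sentence stands in the Trial Summary.
- **Training (7.3).** The resistance sessions are "delivered in one-on-one sessions with a member of the study team three times per week".
- **Assays (8.3).** "Serum inflammatory markers will be measured using the Luminex system, and assessors will be trained". Masking is not mentioned.
- **Strength (8.3).** The 1-RM test uses "incremental increases in load until only one repetition can be completed".
- **Analysis (13.2).** "data analysis will be conducted by the PhD student on both an intention to treat and per protocol basis". The per-protocol set requires complete measurements, at least 75% of exercise sessions and compliance with the diet. Log transformation follows a normality check.

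Section 2.2 also states: "The primary outcome measure will be muscle protein synthesis". Section 2.1 expects the larger improvement in the Pulse group. Section 6.2 has a hospital statistician generate the allocation in advance, concealed in numbered opaque envelopes. Section 16 has participants identified on the Case Report Form by trial number only.

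**The concern.** Whether participants can be masked is one question. Whether the people who handle samples, test strength and analyse data can be masked is another. Section 6.3 answers the first and applies the answer to both. A woman who knows her diet does not prevent a biopsy tube from carrying a code, or a dataset from carrying the labels A and B.

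The study team is small, its duties overlap, and the protocol states which arm it expects to do better. The PhD student is named both as a measurer of outcomes and as the analyst. Arm-dependent judgement could enter through encouragement during a maximal lift, through decisions to repeat an assay or exclude a value, through the choice of transformation, and through the ruling on who followed the diet, for which the protocol gives no threshold. With 10-12 women per arm, a few such decisions can move the Pulse-Spread difference. Section 13.2.5 says the data will inform sample sizes for future studies, so a distorted difference or SD would carry forward.

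**Working it through.** **1. Does any section mask a role that 6.3 leaves open?**

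| Role | Source in Protocol | Covered by the reason in 6.3? | Masked elsewhere? |
|---|---|---|---|
| Participant | 6.3 | Yes | No |
| Staff giving diet plan and training | 7.3 | Not named, but they administer the open intervention | No |
| Day-14 1-RM tester | 2.2, 8.3 | No | No |
| Assay staff (biopsy, saliva, serum) | 2.2, 8.3 | No | No |
| Analyst | 13.2 | No | No |

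The opaque envelopes in 6.2 conceal the allocation until assignment. They mask nobody afterwards. The trial number in Section 16 protects identity. It could serve as a sample code, but the protocol does not say that it hides the arm.

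**2. Where is the exposure greatest?**

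- *1-RM.* The test depends on effort and on the tester's prompting. Sections 8.1 and 8.2 place the baseline test at the pre-trial visit, before allocation, so only the day-14 test is exposed.
- *Analyst decisions.* Exclusions, transformation and diet compliance all involve judgement. The exercise criterion does not, since it is fixed at 75%.
- *Muscle protein synthesis and cytokines.* These are laboratory readings. Judgement enters only through steps such as repeat runs and exclusions, so the exposure is smaller.

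**3. How much could an arm-dependent shift matter?**

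The protocol gives no power calculation, alpha or SD, so there is no figure to reproduce. The calculation below is illustrative. From the protocol: n = 10 or 12 per arm and a two-sample t-test. Assumed: two-sided 5%, no true effect, and a shift of b SD between arms arising only from unmasked handling.

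Standard error of the difference in SD units: √(2/n), which is 0.447 at n = 10 and 0.408 at n = 12. Noncentrality: δ = b / √(2/n). Degrees of freedom: 2n − 2. With c the two-sided 5% critical value and T a noncentral t variable with parameter δ, the false-positive rate is P(T > c) + P(T < −c).

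| n per arm | df | c | b (SD) | δ | P(T > c) | P(T < −c) | False-positive rate |
|---|---|---|---|---|---|---|---|
| 10 | 18 | 2.101 | 0.25 | 0.559 | 0.0763 | 0.0064 | 8.3% |
| 10 | 18 | 2.101 | 0.50 | 1.118 | 0.1838 | 0.0013 | 18.5% |
| 12 | 22 | 2.074 | 0.25 | 0.612 | 0.0847 | 0.0054 | 9.0% |
| 12 | 22 | 2.074 | 0.50 | 1.225 | 0.2153 | 0.0009 | 21.6% |

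An independent simulation of 40,000 t-tests gave 8.2% and 8.9% at 0.25 SD, and 18.8% and 21.6% at 0.5 SD, for n = 10 and 12 respectively. The rounded ranges are therefore about 8-9% and 19-22%.

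**The case against.** The strongest reply has four parts.

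*The shifts are invented.* This stands. The table shows only what a t-test does with a bias of a given size. Nothing in the protocol says that any bias would reach 0.25 or 0.5 SD, and no mechanism is evident for a shift of 0.5 SD in isotope-derived synthesis rates or Luminex readings.

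*The text does not say that everyone knows the arm.* This also stands. A reader might infer from 6.3 that laboratory staff and the analyst are all told the allocation, but no section says so. What the text supports is that these roles are not masked and may know. The inference is stronger for trainers, testers and the analyst, who come from the small open team, than for assay staff.

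*Masking would not stop selective analysis.* This is partly right. A reader might count the freedom to choose between intention-to-treat and per-protocol, or between raw and log data, as harm caused by lack of blinding. It is not: an analyst with A/B labels can compute the same p-values and pick the smallest. That is a matter of prespecification, which may sit in an analysis plan not shown here, and Section 13.2 in any case commits to both populations. Masking removes knowledge of which arm a decision favours; fixing the decisions before unmasking does the rest.

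*The trial is exploratory, unpowered and lightly staffed.* Exploratory status makes a 5% error rate a convenience and not a design target. It does not supply a reason for 6.3 to cover roles its rationale does not reach. The staffing point does limit the remedy. The protocol does not say that a nurse exists who trains none of the women she would test, and at day 14 the participant still knows her diet and supplies the effort, so a masked tester gives only partial protection.

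**Conclusion.** The point holds as a fault in a stated rule, not as a missing detail. Section 6.3 declines blinding for all roles on a rationale confined to participants, and no other section protects the assays, the day-14 strength test or the analysis.

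The size of any resulting bias cannot be estimated from the documents. The illustrative false-positive rates of about 8-9% (0.25 SD) and 19-22% (0.5 SD) rest wholly on an assumed shift, an assumed two-sided 5% level and 10-12 women per arm. They should not be read as the expected error for the primary outcome, where the risk is smaller than for 1-RM and analyst decisions.

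A reader might also infer that masking here would be free. The documents give no costs and do not establish that. They support a narrower statement: the reason given in 6.3 does not stand in the way, and a trial numbering system that could carry the code already exists. The change is worth making because it removes avoidable exposure for little effort.

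**What to change.** Rewrite Section 6.3 as follows:

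1. Restrict the open-label statement to participants and to staff who deliver the diet plans and resistance training.
2. State that biopsy, saliva and serum samples are assayed under a code that hides the arm and, for the day-14 biopsies, the leg. Hiding the leg protects the trained-untrained comparison in 13.2, not the Pulse-Spread one.
3. Place the key with someone who neither measures outcomes nor analyses data, such as the statistician who generated the allocation list, if available for that task.
4. Release the analysis dataset with arms labelled A and B.
5. Require per-protocol membership (including the diet-compliance ruling), exclusions and transformations to be decided and locked before the key is opened.
6. Where existing staffing allows, have the day-14 1-RM conducted to a fixed script by a tester who has not trained that woman and is not told her diet. Where it does not, say so.

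Items 1 to 5 need a protocol paragraph, coded tube labels and a key file; no visit, sample or procedure is added. The downside is that the key must be administered. Item 6 may need staff the trial does not have and is therefore conditional.

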7.1. Treatment

This is not a cTIMP/NIMP study. The protein distribution intervention will be implemented through the manipulation of the participants' existing diet. Protein supplementation may be used for individuals requiring more protein to reach the desired intake, however these will be commercial dietary supplements.

7.2. Treatment Supply and Storage

7.2.1.Treatment Supplies

N/A

7.2.2. Packaging and Labelling

N/A

7.2.3. Drug Storage

N/A

7.3. Dosing Schedule

The protein distribution interventions will be administered through the participants' diets. Participants will be given a diet plan to follow, which will provide 1.2 g.kg⁻¹.day⁻¹ protein in either a Pulse or a Spread distribution.

RET will be consist of a unilateral leg extension programme, delivered in one-on-one sessions with a member of the study team three times per week.

7.4. Drug Interaction or Contraindications

N/A

Trial name:	The effects of protein distribution and resistance exercise training on the muscle of older adults					
Protocol version number:	6.0	version date:	10-Apr-17	Page:	16 of 31	

7.5. Accountability Procedures

Compliance with RET will be assessed by recording attendance to each session. Adherence to diet plans will be monitored using a 3-day food diary completed in the final days of the intervention, and a daily questionnaire in which participants will be asked to state whether or not they have consumed a meal from the diet plan for each daily meal.

7.6. Treatment Modification

N/A

Trial name:	The effects of protein distribution and resistance exercise training on the muscle of older adults				
Protocol version number:	6.0	version date:	10-Apr-17	Page:	17 of 31

8. Trial procedures and assessments

8.1. Summary of assessments

Figure 1 PRODREX summary of assessments

	TRIAL PERIOD						
	Enrolment	Allocation		Post-all	ocation		Close- out
TIMEPOINT**	-28 to -14 days	-14 days to baseline	day 0	week 1	day 7	week 2	day 14
ENROLMENT:							
Eligibility screen (health questionnaire, blood pressure, MMSE)	X						
Informed consent	Х						
Vitals (height, weight, heart rate)	Х						
Unilateral RET familiarisation	Х						
Allocation		Х					
INTERVENTIONS:							
Protein distribution diet			+				-
Unilateral RET			+				—
ASSESSMENTS:							
1-RM strength	Х						Х
3-day food diary		Х				X	
7-day activity monitoring		Х					
Blood sample			Х				Х
Saliva sample			Х		Х		Х
Muscle biopsy			Х				Х
D₂O administration			Х		Х		
Daily compliance questionnaire			+				—

8.2. Schedule of Assessments

-Screening (telephone call): Screening health questionnaire

Trial name:	The effects of protein distribution and resistance exercise training on the muscle of older adults				
Protocol version number:	6.0	version date:	10-Apr-17	Page:	18 of 31

- -Pre-trial visit (visit 0): Consent, health questionnaire, blood pressure measurement, MMSE, vitals measurement (height, weight, heart rate), unilateral knee extension exercise familiarisation (including 1-RM tests), food diary introduced, physical activity monitor attached for 7 days
- -Visit 1 (day 0): Muscle biopsy, blood sample, saliva samples, D₂O administration, unilateral RET session
- -Visit 2-6 (weeks 1-2): Unilateral RET session
- -Visit 7 (day 14): Blood and saliva samples, muscle biopsy (x2), leg extension 1-RM At-home activities:
- -Day 0: Saliva sample
- -Day 7: D₂O administration and saliva samples (x2) (or in CRF if scheduled for training visit)
- -Weeks 1-2: Daily compliance questionnaire
- -Week 2: 3-day food diary

